**General Approach**: We will use linear mixed models (LMM) or generalized LMM (GLMM) to account for clustering. These models will include random practice intercepts to account for correlation of observations from patients within the same practice. For analysis involving repeated measurements, random patient intercepts nested within practice effects will also be included. Unadjusted models will test a fixed intervention effect; adjusted models will include stratification variable used in randomization (practice size) and patient characteristics (age, sex, race, baseline levels). All statistical analyses will be performed in R using glmmTMB and lme4 packages to fit discrete-time survival models, GLMM, and

LMM and use the marginal effects package to estimate adjusted average responses and contrasts.

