Primary clinical outcome (Aim 2: eGFR decline ≥40% or ESRD): Our primary analysis will use discretetime survival methods to examine the occurrence of the composite endpoint at 6-month intervals from baseline. To determine progression at each of these discrete time points, the average of all eGFR measurements within a +/- 3-month window will be used in order to account for random eGFR fluctuations and potential ascertainment bias. We will employ generalized GLMM with complementary log-log link with random practice intercepts to account for practice-level clustering. This is analogous to a Cox model with frailty for continuous-time survival data (i.e., a random effects survival analysis model). The unadjusted model will include fixed effects for intervention, and time. The functional form of time (categorical or continuous with restricted cubic splines) will be selected based on the Akaike Information Criteria (AIC). Adjusted models will include pre-specified patient (age, sex, race, baseline eGFR) and practice variables (practice size). MMWD, being moved to hospice care, or mortality will be treated as competing events. Those that did not reach any endpoint will be censored at the end of study (July 31, 2022). In secondary analysis, we will use eGFR as a continuous variable and include random patient intercepts nested within random practice intercepts. The unadjusted model included fixed effects for intervention, time, and treatment by time interaction. We will compare the rate of eGFR decline over time between groups. As sensitivity analyses, we evaluated a) smoothing-spline mixedeffects models since eGFR trajectories may be nonlinear, and b) requiring 2 consecutive eGFR values below the 40% decline/ESKD threshold.

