Secondary process of care outcomes (Aim 1): To assess the intervention effect on hypertension control, we will compare the mean outpatient systolic blood pressure (SBP) between intervention and control at each 6-month time point using LMM with fixed effects for treatment, time, and treatment by time interaction. At each time point, the average of all BP measurements within a +/- 3-month window will be used to account for random fluctuations. As an alternative approach, we will analyze BP as a binary outcome defined by achieving BP goal of <140/90 mm Hg or <130/80 mm Hg via GLMM with logit link and binomial family. If linearity of time is reasonable, we will compare the slopes between intervention and control. These models will include random patient intercepts nested within random practice intercepts and will be adjusted for pre-specified covariates (age, sex, race, and practice size). In examining medication use, we will compare the average medication exposure days between the arms using LMM with random practice effect. For each medication class, the number of exposure days will be determined by counting the number of days from medication order start date to either the discontinuation date, survival endpoint date (progression, ESKD, death/hospice, MMWD) or study end date, whichever comes first. (refer to Table 1 for details). To account for potential overdispersion, we will also fit count models including Poisson, generalized Poisson, and negative binomial mixed models and select the final model based on minimum Akaike Information Criteria (AIC) or Bayesian Information Criteria (BIC). If count models provide better fit, we will report the rate of exposure days per year for each medication. We will adjust for baseline medication exposure days in addition to pre-specified covariates with the log of the number follow-up days as offset. In post-hoc analyses, we will evaluate the effect of intervention on albuminuria minimization among patients with at least one urine-albumin-tocreatinine ratio (UACR) measure during the study period. Similar to the approach we used for examining changes in eGFR, we will fit a mixed effects model utilizing all available UACR for each patient adjusting for age, sex, race, baseline eGFR and practice size. We will also adjust for diabetes since we found that it is associated with having at least one UACR measure during the study period. Changes in UACR from baseline to 18 months (approximately the median follow-up time) were calculated by group, and between group differences were compared using contrasts.

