
**Exploratory analyses:** Although this study is not powered to conduct subgroup analyses, we will perform analyses stratified by age, sex, CKD stage, DM status, HTN with baseline BP (>140/90 mmHg or >130/80 mmHg), and ACEi/ARB in albuminuric patients, or SGLT-2i use to explore whether heterogeneous intervention effects exist among these subgroups. Subgroup by race will also be examined.

Missing Data: The extent of missing data will be described. We will investigate the randomness of

missing data using available information on patient and provider characteristics to identify possible covert missing data mechanisms. The analytical models used can handle data that are missing at random, but other strategies to handle missing data (multiple imputation, selection models, pattern-mixture models) will also be implemented. In addition, adjusted LMM or GLMM will be used to account for variables associated with missingness.

Table 1. Determination of outcomes and covariates based from electronic health record (EHR)

	Determination from EHR	
General principles		
Baseline time point (T0)	Office or telemedicine encounters with the PCP after the date the patient was determined to be eligible will be extracted. The first PCP encounter within 1 year of the date of eligibility determination will be used as the baseline time point (T0).	
Outpatient records	Outpatient data will be extracted from the EHR.     Laboratory results or vital records obtained within a span of 2 consecutive days will be excluded, as these are more likely to stem from inpatient encounters.	
Primary outcome		
Composite of ≥40% decline in eGFR from baseline or ESKD	The CKD-EPI creatinine (2021) equation will be used to calculate eGFR. (6)	

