### **Summary of Major Revisions to the SAP**

The major changes in the SAP and their underlying reasoning are itemized below. These determinations were made prior to the initial disclosure of the study outcomes to the research team in March 2023.

- Establishment of Baseline Date: The baseline date was set as the first primary care provider (PCP) visit within one year of the eligibility determination date. This choice was made to ensure a common starting point (time 0) for both study arms, which is crucial for conducting time-to-event analyses.
- eGFR Calculation: To align with current clinical practice, the CKD-EPI 2021 equation was adopted for eGFR calculations.
- Competing Events: Events such as Medication Management Without Dialysis (MMWD), transition to hospice care, or mortality were considered as competing events as these endpoints may informatively censor the primary outcome (progression or ESKD). An exploration of the intervention's impact on mortality and the composite of progression, ESKD, or mortality was planned.
- Adjusted Models: Efficiency enhancement was pursued through the inclusion of pre-specified covariates in adjusted models: age, sex, race, and baseline eGFR. These factors were anticipated to be linked with the primary outcome.
- Subgroup Analyses: Subgroups were formed based on age, sex, and CKD stage. The aim was to scrutinize whether treatment effects differed across diverse patient demographic and clinical characteristics.
- SAP Layout and Detail Enhancement: The SAP's layout was restructured, and more comprehensive details about variable extraction from EHR were added.

Further alterations were enacted following the unveiling of the initial study results to the research team in March 2023.

- Hypertension Control Definition: To remain consistent with contemporary guidelines, a blood pressure (BP) goal of <130/80 mm Hg (SBP/DBP) was integrated as an alternate hypertension control endpoint. This definition was also added to subgroup analyses related to the primary outcome.
- Medication Exposure Days Calculation: To limit missing data in medication exposure days
  calculation, chronic medications were assumed to be active for one year from the medication
  start date when discontinuation date is unknown. For NSAIDs, medication refills were used as
  these are not consistently prescribed for extended periods.

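### The final SAP asks whether intervention effects differ between subgroups but plans only stratified analyses, with no treatment-by-subgroup interaction or between-stratum contrast

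*Combined protocol and SAP*

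**What the plan says.** The Exploratory analyses paragraph of the Final Statistical Analysis Plan gives the method: "we will perform analyses stratified by age, sex, CKD stage, DM status", followed by hypertension with baseline BP at two cut-offs, ACEi/ARB in albuminuric patients, and "SGLT-2i use to explore whether heterogeneous intervention effects exist among these subgroups". Race is then added. That is eight factors. The paragraph opens with a caveat: "Although this study is not powered to conduct subgroup analyses".

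The Summary of Major Revisions to the SAP states the purpose of the age, sex and CKD stage subgroups: "The aim was to scrutinize whether treatment effects differed across diverse patient demographic and clinical characteristics". It also refers to subgroup analyses of the primary outcome when it describes the added 130/80 BP definition.

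The models that could carry a subgroup term are these:

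- Primary composite outcome: "The unadjusted model will include fixed effects for intervention, and time". The adjusted version adds listed patient covariates and practice size.
- Continuous eGFR: "The unadjusted model included fixed effects for intervention, time, and treatment by time interaction".
- SBP: "LMM with fixed effects for treatment, time, and treatment by time interaction".
- General Approach: the software will "use the marginal effects package to estimate adjusted average responses and contrasts". This is not tied to subgroups.
- UACR: contrasts between arms, not between strata.

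**The concern.** Whether effects differ across strata is a question about one quantity: the difference in treatment effect, or the ratio of hazard ratios on the multiplicative scale. Analysing each stratum separately produces two or more stratum effects but not that quantity or its uncertainty. The SAP also gives no rule for judging from the stratum results whether effects are heterogeneous.

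The risk is that strata are compared informally, with one significant and the other not taken as a sign of heterogeneity. Each stratum has fewer events than the whole trial and so lower power, which means this pattern arises often when the effect is identical in both. With eight factors and the primary outcome in scope, a spurious subgroup statement is a real possibility.

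**Working it through.** **Is the contrast planned anywhere?** Setting the final SAP's sections side by side, the primary model has intervention, time and covariates; the continuous eGFR and SBP models add treatment by time only; the General Approach mentions contrasts in general; and the UACR contrasts compare arms. None involves treatment by subgroup. The gap is in the method and does not depend on any calculation. The figures below only show its consequence.

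**The plan's own figures.** The SAP gives no figure for subgroups. From its Sample Size section I use two-sided α = 0.05, at least 80% power at HR 0.64 with N = 1,102 (individually randomised), ICC 0.01 and 19 patients per practice.

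- Required total: 1,102 × (1 + 18 × 0.01) / 0.80 = 1,626, against the stated 1,653 (1.7% lower).
- Power at N = 1,102 (Schoenfeld, exponential event times): 74.5% if only 24-month proportions of 0.15 and 0.10 count (138 events), and 85.6% with 18 months' accrual plus 24 months (183 events). The 80% used below lies between these.

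**Overall standard error.** SE(log HR) = |ln 0.64| / (1.960 + 0.842) = 0.446 / 2.802 = 0.159.

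**Assumed strata.** One binary patient-level factor divides the whole cohort 50/50 or 30/70; the SAP gives no subgroup sizes. Each split is computed in two ways:

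- Without clustering, stratum power = Φ(2.802·√share − 1.96).
- With clustering (factor spread evenly over practices), the variance of a stratum effect relative to the overall variance is [0.01 + 0.99/(19·share)] / [0.01 + 0.99/19], and the relative covariance between strata is 0.01 / [0.01 + 0.99/19].

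**Uniform HR of 0.64**

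| Case | Stratum powers | Correlation | Exactly one significant |
|---|---|---|---|
| 50/50, no clustering | 0.508, 0.508 | 0 | 0.500 |
| 30/70, no clustering | 0.335, 0.650 | 0 | 0.550 |
| 50/50, ICC 0.01 | 0.542, 0.542 | 0.088 | 0.469 |
| 30/70, ICC 0.01 | 0.370, 0.671 | 0.080 | 0.523 |

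Without clustering the last column is p₁(1 − p₂) + p₂(1 − p₁); for example, 2 × 0.508 × 0.492 = 0.500. With clustering it comes from the bivariate normal distribution.

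**Other uniform effects, over the four cases.** Exactly one stratum is significant in 0.371–0.385 of trials at HR 0.75, 0.198–0.201 at HR 0.85, and 0.095 with no effect (2 × 0.05 × 0.95). A 5% interaction test gives 0.05 in every row.

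**What the interaction estimate would show**

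| Case | SE of log ratio of HRs | Power for a ratio of 0.64 | Ratio for 80% power, exp(−2.802·SE) |
|---|---|---|---|
| 50/50, no clustering | 0.319 | 0.288 | 0.410 |
| 30/70, no clustering | 0.348 | 0.250 | 0.378 |
| 50/50, ICC 0.01 | 0.292 | 0.334 | 0.442 |
| 30/70, ICC 0.01 | 0.318 | 0.289 | 0.410 |

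**What a reader could recover.** Suppose stratum estimates and SEs are published and the reader ignores that strata share practices. In the clustered case the SE becomes 0.305 (50/50) or 0.331 (30/70). The 95% interval is then the estimate divided and multiplied by exp(1.96·SE): 1.82 instead of 1.77, or 1.91 instead of 1.87. The approximate test has true size 0.040 or 0.042, slightly conservative.

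**The case against.** The strongest reply has four parts.

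- **No significance rule is stated.** The SAP calls these analyses exploratory and unpowered, so the 47–55% belongs to a reading the plan does not adopt. This stands. The figure is conditional and also depends on the assumed effect. It does not remove the main point, which is that the plan asks about a difference and specifies no estimate of it.
- **Readers can do it themselves.** For a binary factor little precision is lost, as the interval factors show. But this needs stratum SEs or intervals. The SAP commits to reporting under the CONSORT extension for cluster trials but does not itself say these will be given. A factor with more than two levels needs a joint test that stratum results do not supply directly.
- **Interaction tests bring multiplicity and low power.** Eight independent tests at 5% give a 1 − 0.95⁸ = 34% chance of at least one false positive. This is true and should be stated with the results. It is still below the 1 − 0.905⁸ = 55% from comparing significance across eight binary factors with no effect, also treated as independent. Low power argues for showing the estimate with its wide interval and against leaning on a p-value.
- **The general contrasts statement could cover it, and results are already known.** The software can produce the contrast, but nothing directs it to subgroups. The timing means the change cannot restore prespecification and has to be disclosed as post hoc.

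**Conclusion.** The concern holds, as a low-severity improvement. The final SAP poses a question about differences between strata and names a method that does not estimate them. Under significance-by-stratum reading, a uniform HR of 0.64 would look heterogeneous in about half of trials (47–55%), falling to 37–39% at 0.75, about 20% at 0.85 and 9.5% with no effect.

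These figures rest on the SAP's 80% power at HR 0.64, a single binary factor over the whole cohort, assumed 50/50 or 30/70 splits, 1:1 allocation and, where clustering is included, even spread over practices with ICC 0.01. They do not carry over to ACEi/ARB in albuminuric patients or to factors with more than two levels. The exploratory label and the stated lack of power keep the harm small.

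**What to change.** For each subgroup factor, add treatment-by-subgroup terms to the clustered model already specified for that outcome:

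- one term for a binary factor;
- several terms with a joint test for a factor with more levels;
- treatment-by-subgroup-by-time terms if the eGFR slope or repeated SBP models are also examined by subgroup.

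Report the ratio or difference of effects with its 95% CI, derive the stratum effects from the same model, and base any statement about heterogeneity on that contrast. The software named in the General Approach can produce it.

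Keep the exploratory label, state how many interactions were examined, and say that a non-significant interaction is not evidence of a uniform effect: power is only 25–33% for a ratio of HRs of 0.64, and 80% power needs a ratio of 0.38–0.44. Disclose that the terms were added after results were unveiled in March 2023, as the Summary of Major Revisions already does for other changes.

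The cost is a short SAP addition and a few model terms, with no new data.

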### V. Data collection and Outcomes

Routinely collected EHR and administrative data will be abstracted for outcomes assessment as shown in Table 2. PCP practice level data will be obtained from public records.

Table 2: Key variables and covariates for usual care and intervention patients

Variables	Variable descriptions	Data source details
Renal function and rate of change in renal function	
 
Baseline serum creatinine – most recent creatinine from date of study enrollment visit with PCP up to 365 days prior to the visit.
 
Baseline eGFR – Calculated using CKD-EPI.
 
Baseline rates of change in eGFR - determined from baseline eGFR and prior eGFRs between 365 to 730 days before the baseline value.
 
	EHR (restricted to outpatient labs)
Socio- demographics	
 
Age, gender, race, ethnicity, marital status, insurance, and zip code for linkage with neighborhood median household income.
 
Baseline values defined on the date of baseline visit
 
	EHR
Comorbid conditions	
 
DM, HTN, hyperlipidemia, CAD, cerebrovascular disease, peripheral vascular disease, CHF, arrhythmia, gout, chronic lung disease, chronic liver disease, mood disorder, and malignancy.
 
Baseline values defined on the date of baseline visit and using a 24 month "look back" period.
 
	Phenotypes using administrative & clinical codes, meds, & lab values validated in local EHR. 12,38,39
Blood Pressure	
 
Baseline BP - mean outpatient BP from the date of the baseline study visit with the PCP until 180 days prior to the baseline visit.
 
Follow-up BP - all outpatient BPs after patient enrollment
 
	Office visit vital signs recorded in the EHR
Medication use	tion  • RAASi, NSAID and other medications deemed a potential safety concern (e.g., allopurinol, gemfibrozil, glyburide, metformin, etc.)  • Medication related problems and drug record discrepancies	
Laboratory values		
Urine albuminuria	
 
Quantitative urine albuminuria - most recent ACR from the baseline visit up to 365 days prior to the visit.
 
Urine dipstick albuminuria - median of outpatient values available from the date of baseline visit up to 365 days prior to the visit.
 
	Outpatient lab values from EHR

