### Secondary outcomes - Process of care outcomes

1. HTN control. Outpatient, sitting BP values measured during each outpatient encounter and recorded in the EHR. BP will be treated as a continuous variable. To minimize

- ascertainment bias, we will use 6-month ascertainment windows to determine an average BP for each patient for each 6-mo period. Patients lacking an outpatient value will have their last value carried forward
- 2. Use of RAASi. Will be determined by active use of an ACEi or ARB based on the EHR medication list at each outpatient encounter. Analyses will compare cumulative person-time exposure during the study.
- 3. Medication safety. We will examine the rates of use of several high-risk medications that can be associated with adverse outcomes in progressive CKD. Medication exposure will be determined by presence of the specified medication on the patient's EHR medication list at each outpatient encounter. Analyses will compare cumulative person-time exposure during the study.
  - a. Use of NSAIDs: use examined for all study patients
  - b. Use of glyburide: use examined for all diabetic study patients
  - c. Use of metformin: use examined for diabetic study patients with eGFR<30
  - d. Use of gemfibrozil: use examined for all study patients with eGFR<30.

Exploratory outcomes. Mortality, hyperkalemia, and health utilization (i.e., costs) including hospitalizations, emergency department visits, and outpatient encounters will be ascertained by a combination of EHR and administrative data from the UPMC health plan. The accessibility of administrative data that captures events outside the health system and supplements the EHR is a unique and complementary resource that will be leveraged in future study analyses.

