Some of these interventions may pose a small psychological risk to the patient. Patients who were previously unaware, may become aware of their CKD status. However, the patient will have discovered the presence of a serious illness with potentially severe complications and (most importantly) available treatments. Further studies to delineate the exact etiology of the CKD and subsequent treatments can be initiated. The intervention may assist with proper medication dosing, avoidance of nephrotoxic medications, and avoidance of potentially risky procedures (imaging with intravenous contrast or gadolinium containing compounds). The intervention may also help delay the need for dialysis and ensure patients are prepared for dialysis if it becomes necessary. In addition, PCPs can choose to defer discussions and treatment if they feel a patient is unlikely to have high- risk CKD or benefit from any of the aspects of the intervention. The presently available alternative approach is to continue current practice with suboptimal PCP treatment of CKD.

While it is unlikely that systematically providing evidence-based CKD recommendations to PCPs of high risk patients by board certified nephrologists and pharmacists will worsen overall clinical outcomes, we will monitor several safety signals. We will gather these safety data annually through the EHR, minimizing additional patient or study cost burden. Potential adverse events that will be monitored include:

- 1) Rates of hyperkalemia (K>5.5, K>6)
- 2) Rates of emergency department visits and hospitalizations
- 3) Rates of death.

Tests and treatments implemented by PCPs based on nephrologist's or pharmacist's recommendations are likely to be relatively inexpensive and non-invasive and should expose the patient to minimal financial or bodily risk. *The board certified PCP is the final arbiter of medical decisions regarding their patients*.

No patient will be excluded based on gender, race, or ethnicity. However, we are restricting the intervention to UPMC health plan patients (including UPMC Medicare Advantage) for several reasons. First, this allows us to inform PCPs and patients that we have partnered with the patient's insurer in an effort to optimize care, thereby mitigating potential financial concerns. Second, the health plan's support will allow us to supplement EHR data with administrative

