data to adjudicate outcomes while minimizing misclassification. Our findings will inform future efforts to extend the intervention while preserving fiscal sustainability.

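### Final SAP Table 1 names only the EHR as the source for ESKD codes, hospice and death, although the protocol plans health-plan data for outcome adjudication, so events outside the system can be missed

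*Combined protocol and SAP*

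**What the plan says.** **Protocol.** Section IV (Eligibility) requires health plan insurance. Section VI, Potential Risk, explains why: "we are restricting the intervention to UPMC health plan patients (including UPMC Medicare Advantage) for several reasons". The first reason is partnership with the insurer, "thereby mitigating potential financial concerns". The second is that "the health plan's support will allow us to supplement EHR data with administrative" "data to adjudicate outcomes while minimizing misclassification" (one sentence, split by a page break). Section V opens with "Routinely collected EHR and administrative data will be abstracted for outcomes assessment as shown in Table 2". The exploratory-outcomes paragraph of Section V says that mortality and utilization, among others, will be "ascertained by a combination of EHR and administrative data from the UPMC health plan". It adds that these data are accessible and capture events outside the system, but places their use in later analyses of the study.

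**Final SAP.** Table 1 is titled "Determination of outcomes and covariates based from electronic health record (EHR)", and its column header also names the EHR as the source. Under it:

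- ESKD is an averaged eGFR below 10 ml/min, or ICD-10 or CPT codes for ESKD or transplant.
- MMWD and hospice/death come from ICD-10 codes or the date of death.
- Medication exposure comes from EHR orders, except that NSAID days come from refills.
- Patients with no EHR record at a follow-up point are treated as not having reached an endpoint and are censored.

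Neither the Final SAP nor its Summary of Major Revisions mentions claims, administrative data or the health plan.

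**The concern.** The protocol itself says what the second data source is for: it sees events that the EHR does not. The trial narrowed its population partly to obtain that source. An analysis plan that omits it, without recording the omission, accepts a gap that the protocol had identified and planned to close.

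At stake are the coded part of the ESKD component, the competing events, and the planned exploration of mortality and of progression, ESKD or mortality combined. The Summary of Major Revisions made MMWD, hospice and death competing events because they may censor the primary outcome informatively. A death that is not recorded and is handled as ordinary censoring brings that problem back.

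**Working it through.** **1. Sources side by side.**

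| Item | Protocol | Final SAP Table 1 |
|---|---|---|
| Outcomes in general | EHR and administrative data (V); administrative data to adjudicate (VI) | EHR (title and column header) |
| ESKD | eGFR below 10 (V, Primary Outcome) | eGFR below 10, or ICD-10/CPT codes |
| Mortality | EHR plus health-plan data (V, exploratory); also EHR safety monitoring (VI) | Date of death, origin not stated |
| Hospice, MMWD | Not specified as follow-up outcomes | ICD-10 codes |
| Medication | EHR medication list (V) | EHR orders; refills for NSAIDs, origin not stated |

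The direct conflict is with the protocol's general statements and, for mortality, with a specific one. For medication the two documents agree that the EHR is the source.

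**2. One patient traced through the rules.** Take an insured patient who starts dialysis or dies elsewhere between two landmarks. No in-system creatinine falls in the window and no EHR code is entered. Table 1 then treats the patient as endpoint-free and censors. It does not say whether censoring falls at the last record or at study end (31 July 2022). In the first case the patient leaves the risk set before the event; in the second, event-free time is also credited. The event is lost either way.

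**3. Overlap within the composite.** A 40% decline from baseline *b* means reaching 0.6 × *b*. This is at or above 10 when *b* ≥ 10 / 0.6 = 16.7 ml/min. For those patients an eGFR below 10 already meets the decline criterion. An outside dialysis start is therefore lost to the primary outcome only if no earlier in-system window average had met the 40% decline.

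**4. Competing events.** The SAP does not say whether the competing-event analysis is cause-specific. If it is, a recorded death and a censored one both remove the patient from risk, and the effect on the hazard comparison is limited. Cumulative incidence, mortality and the composite that includes mortality would still be affected.

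**5. The plan's own figure, then an illustration.** Inputs (Final SAP, Sample Size): 1,102 patients under individual randomization, ICC 0.01, cluster size 19, 20% attrition, HR 0.64, two-sided α 0.05, at least 80% power.

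- Design effect: 1 + (19 − 1) × 0.01 = 1.18.
- 1,102 × 1.18 = 1,300.4, and 1,300.4 / 0.80 = 1,626 rounded up, against the stated 1,653 (1.6% lower). With the design effect rounded to 1.2, 1,102 × 1.2 / 0.80 = 1,653 exactly.
- Events for 80% power (Schoenfeld): 4 × (1.960 + 0.842)² / (ln 0.64)² = 158. This count is derived, not stated in the plan. Clustering is carried by the design effect.

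The documents give no share of events occurring outside the system, so the shares below are assumptions. If a share *m* of all composite events is missed equally in both arms, power = Φ(√(158(1 − m)) × |ln 0.64| / 2 − 1.96):

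| Assumed share missed | Power |
|---|---|
| 0% | 80.1% |
| 5% | 78.1% |
| 10% | 75.8% |
| 20% | 70.8% |
| 30% | 65.1% |

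If the share differs by arm, the observed HR is roughly the true HR × (1 − m_intervention) / (1 − m_usual care). With 10% missed in one arm only:

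- missed in usual care: 0.64 / 0.9 = 0.71, and a true 1.0 becomes 1.11;
- missed in the intervention arm: 0.64 × 0.9 = 0.58, and a true 1.0 becomes 0.90.

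These shares apply to the whole composite. Losing the same share of coded ESKD events alone would matter less, because eGFR decline is also a component.

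**The case against.** The strongest reply is that the protocol never specified the primary outcome from claims. Its ESRD definition was an eGFR threshold, so adding ICD-10 and CPT codes widens ascertainment. The protocol also puts administrative data under exploratory outcomes and defers them to later analyses, and its safety section gathers deaths through the EHR. All of this stands. It shows that the protocol is itself inconsistent, but it does not remove the two statements that administrative data will serve outcome assessment and adjudication.

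The plan also has safeguards: BMP reminders in both arms, averaging within windows, blinded outcome assessment and missing-data models. The reminders and averaging address unequal eGFR measurement. None of the four recovers a dialysis code, hospice entry or death that the EHR never held.

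Four stronger readings are tempting, and the documents do not support them:

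- **Claims are expressly excluded.** This is an inference from the table's title, its header and the absence of another source. The origin of CPT codes, death dates and NSAID refills is unstated.
- **The enrolment restriction brings no benefit.** The insurer partnership is a separate stated reason.
- **The bias runs against the intervention.** Its scheduled contacts could make EHR capture more complete, but no figure shows unequal capture, and the e-consult does not involve patient contact.
- **The size can be read from the 75% with an eGFR every 6 months or the 20% attrition.** A window without a laboratory value is not care elsewhere, and attrition may include people who left the plan, whom claims would not cover.

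**Conclusion.** The point holds as a gap between a planned data source and the analysis plan, with a practical consequence. Followed as written, Table 1 can miss dialysis, transplant, hospice and death occurring outside the system among patients who remain insured, and it then treats those patients as endpoint-free and censored. The documents give neither the size nor the direction. The power and hazard-ratio figures above are illustrations under assumed shares.

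The conclusion rests on two assumptions: that Table 1 means what its title and header say, and that some insured patients receive care outside the system, as the protocol's account of administrative data implies. A reader might also infer an error in medication exposure. That is not supported: the protocol already used the EHR list, and NSAID days already rest on refills.

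**What to change.** 1. In Final SAP Table 1, ascertain ESKD/dialysis, transplant, hospice and death as the first occurrence in the EHR or health-plan claims. End follow-up for these coded events at plan disenrolment if that precedes study end.
2. Outcomes were first disclosed to the team in March 2023. If the primary definition is already fixed, keep the EHR-based result and report the claims-supplemented one beside it as a labelled sensitivity analysis.
3. State the source of the ICD-10 and CPT codes, the death dates and the refill records.
4. Reconcile the protocol's Section V opening, its exploratory-outcomes paragraph and Section VI, Potential Risk, on whether administrative data serve this analysis or later ones. If claims were dropped, give the reason in the Summary of Major Revisions.
5. Optional, and not a correction: a pharmacy-fill sensitivity analysis of ACEi/ARB, glyburide and metformin exposure.

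The cost is SAP wording and linkage programming, using data that the protocol describes as accessible. Claims lag may leave the last months incomplete, and claims cannot recover patients who leave the plan.
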